1.1 Concurrent chemo-radiotherapy

Lung cancer is the major cause of cancer-related death in Europe and North America. About 75% to 80% of lung cancer is non-small-cell cancer (NSCLC) with approximately 40% of patients presenting with locally advanced disease. In patients with no malignant pleural effusions, the treatment options have been irradiation up to 60-70 Gy against the primary lung tumor and lymph nodes in mediastinum resulting in a median survival of 6 to 11 months and 5 years survival of 5%. The treatment have until recently consisted of irradiation of the tumor bed and areas around with high risk of relapse. The treatment has now being optimized by giving chemotherapy either before irradiation or concomitant with radiation or both. The irradiation technique have been improved by introduction of 3D-CT-scan based planning technique, and the prognosis have been somewhat improved. Data from Odense shows a 5 year survival rate of 16% at 5 years (1). The treatment of choice for locally advanced NSCLC is radiotherapy combined with chemotherapy since trials using inductions chemotherapy and/or concomitant chemotherapy have demonstrated increased median survivals to 13-15 months with a 5 years survival of 10-20%. The rationale for using of inductions chemotherapy has been to reduce the treatment volume by reducing the tumor burden and to eradicate micro-metastases.

A significant problem in the treatment of local advanced NSCLC is a high rate of local failure of up to 45% without distant metastases after irradiation. In 200 patients with NSCLC stage III treated in Odense the 1 year survival was 61%. 112 of these had received a platinum based induction chemotherapy regimen, and 3 had concomitant therapy with Taxotere. The local failure free survival was 70% 9 months after start of irradiation and 43 % after one year (unpublished data).

The poor local control is partly due to the tumors content of radio-resistant cells in hypoxic areas of the tumor. The radio-resistance is in part due to an up-regulation of the epidermal growth factor receptor (EGFR). The radio-resistance of the tumor cells can be overruled at least from a theoretical point of view by using concomitant treatment with drugs, which either can bring the tumor cells in phases of the cell cyclus in which they are more sensitive to irradiation (G₂- and M-phase) or specifically kill the hypoxic cells.

Concurrent chemo-radiation is considered to be standard in radiation of local-regional advanced NSCLC (2). However, a number of patients are unfit or refuse chemotherapy. In these cases radiotherapy at present has to be administered by itself.

1.2 EGFR blockage of the radiation response

Increased expression of EGFR has been observed in several solid tumors, including NSCLC and squamous cell carcinoma of the head and neck. EGF binds to the EGFR stimulating autophosphorylation of the intracellular tyrosine kinase domain of the receptor. Activation of the EGFR signal transduction pathway enhances cellular processes involved in tumor growth and progression, including the promotion of proliferation, angiogenesis, invasion, and metastasis.

Blockage of the EGFR signaling pathway has been shown to enhance the radiation response in cell lines and in clinical studies. The blockage can be done by anti-EGFR monoclonal antibody, or by tyrosine kinase inhibitors like Tarceva (Erlotinib). Studies have demonstrated that blockage of the EGFR with the monoclonal antibody Cetuximab (IMC-C225) enhances radiation response in squamous cell lines of the head and neck (3) and in mice carcinomas (4). Blockage of the EGFR signaling pathway by tyrosine kinase inhibitors increased radiation response in human xenografts in mice (5), bladder carcinoma cell lines (6) and breast cancer cell lines (7).

In clinical studies, tumors arisen from several different organs have been studied, and increased expression of EGFR has been correlated with disease progression and poor overall outcome after

radiotherapy. In a retrospective study of 155 patients with head and neck cancer treated with standard radiotherapy the level of EGFR expression had highly significant correlation with the survival rates and loco-regional control, but not with the incidence of distant metastasis (8). In a randomized phase III study including 424 patients diagnosed with loco-regionally advanced squamous cell carcinoma of the head & neck, and addition of cetuximab to radiation therapy, a statistically significant prolongation in overall survival was obtained without augmenting the radiation side-effects (9).

A small phase I study of daily Tarceva and concomitant chemo-radiotherapy has been carried out in esophageal cancer (10). The chemotherapy consisted of Cisplatin and 5-FU. The radiation dose was 50.4 Gy in fractions of 1.8 Gy. Doses of 50 mg, 100 mg, and 150 mg Tarceva daily were well tolerated. The major toxicity was esophagitis (9% grade 4), diarrhea, skin rash, nausea, and dehydration. No excess lung toxicity was experienced.

Preliminary data of a small randomized phase II study of \pm Tarceva 150 mg/day administered concomitant with 66 Gy /33 F in patients unfit for chemotherapy indicated that this schedule was feasible (11). In 22 patients treated with concurrent Tarceva and radiation evaluable for toxicity, no case of grade 3-4 pneumonitis or esophagitis was observed (information on poster).

1.3 Tarceva

Tarceva (Erlotinib hydrochloride) is a quinazolinamide that inhibits the intracellular tyrosin kinase domain of the EGFR. It is formulated as immediate release tablets. Bioavailability of Erlotinib following a 150 mg oral dose is about 60% (and almost 100% if taken together with food) and peak plasma levels occur 4 hours after dosing. The median half-life is 36 hours, and the time to reach steady-state plasma concentration is 7-8 days (12). Smokers have a 24% higher rate of Erlotinib clearance. Erlotinib is metabolized by the liver cytochrome P450 system primarily by CYP3A4 which may be a cause of interaction with other drugs.

2. Objectives of the study

The trial is a phase II study of daily Tarceva combined with definitive radiotherapy in inoperable locally advanced non small cell lung cancer (stage IIB-IIIB).

The objective of the phase II trial is to examine Tarceva concomitant with curatively intended irradiation 66 Gy (2 Gy x 33 F, 5 F per week):

Primary endpoint

- Local failure free survival at 9 months after start of radiotherapy evaluated at CT scan.

[figure not shown]
Secondary endpoints

- Toxicity
- Local tumor control by CT-scan
- Overall response rate (CR + PR).
- Local tumor control at 9 months evaluated by PET-CT
- Overall survival
- Disease free survival
- Late toxicity

3. Study design and dosing regimen

3.1 Study design

The treatment plan is consisting of radiation; 3-D conformal radiotherapy given together with Tarceva 150 mg/day. Induction chemotherapy may be used. No concurrent chemotherapy may be used.

Figur 1: Time line in the study

3.2 Dosing regimen

Tarceva will start at the day of the radiation in daily dose of 150 mg. The last dose will be given the day the radiotherapy stops. Tarceva will be administered continuously for approximately 6.5 weeks. Drug accountability will be registered according to Good Clinical Practice (GCP). The radiotherapy is only administrated 5 days a week.

3.3 Interruption or discontinuation of Tarceva in the individual patient.

Toxicity grading will be according to the CTC version 3.0. Following dose adjustment for drug-related toxicity is recommended: If any grade III or worse toxicity including skin toxicity or diarrhea occurs, the Tarceva will be paused till toxicity has resolved to a grade II or better. The Tarceva will be resumed in a dose of 100 mg if the dose before pausing was 150 mg, or 50 mg if the dose was 100 mg. If the dose was already 50 mg, the Tarceva will not be resumed. The radiotherapy should be continued. For management of radiation complication during therapy see section 8.2. Management of Tarceva related toxicities see Appendix 4.

4. Planning of radiotherapy

The planning technique is based on ICRU62 recommendations, and the DOLG 2009 criteria. The planning may, however, make use of 4-D scans, and that will influence the margins, se below. The prescribed dose is 66 Gy /33 F / 5 F per week. If induction chemotherapy has been administered radiation may start within 2-5 weeks after last dose of chemotherapy.

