8.2 Expected adverse effect

Tarceva: The most common, expected adverse events for Tarceva include: Rash, pruritus, dry skin, diarrhea, nausea, vomiting, stomatitis, abdominal pain, fatigue, dyspnoe, cough, anorexia, infection, conjunctivitis, and keratoconjunctivitis sicca.

Irradiation: The toxicity of irradiation of NSCLC is determined of the dose and treatment volume of organs at risk. These are as followed:

Organs at risk	Acute (1-12 weeks)	Late >3 months
Lung ¹	Pneumonitis (cough, dyspnoe, fever)	Fibrosis (cough, dyspnoe)
Esophagus ²	Swallowing difficulties, pain	Stenosis (swallowing difficulties)
Heart	Pericarditis ⁴	Fibrosis
Skin	Edema, skin rash	Fibrosis, telangiectasies
Spinal cord	Lhermitte sign ³	Radiation myelitis ⁴ (neurological deficits)

¹: The risk of acute pneumonitis may increase in irradiation when Tarceva is combined with -radiation. The risk of pneumonitis increases with the V₂₀ of the lung. The symptoms may develop before stop of irradiation. The treatment in the case of pneumonitis is steroid ± antibiotics.

² Occurrence of esophagitis is connected to treatment volume and concomitant therapy.

³ Lhermitte sign is a transient self-limiting symptom of radiation impact on the cervical spinal cord.

⁴Pericarditis and radiation myelitis: no cases of these side effects are expected in this study.

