8.3 Management of radiation complications during radiotherapy

In case of grade 3 or worse esophagitis or pneumonitis, the administration of Tarceva will be terminated for that patient.

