Appendix 4: Dosage guidelines for management of study drug related toxicities

Toxicity, CTC Grade	Study Drug Dosage Modification	Guideline for Management
Diarrhea		
Grade 1	None	Consider Loperamide (4 mg at first onset, followed by 2 mg every 2 – 4 hours until diarrhea free for 12 hours) Appropriate rehydration
Grade 2	None	Loperamide (4mg at first onset, followed by 2 mg every 2 – 4 hours until diarrhea free for 12 hours) Appropriate rehydration
Grade 3	Interrupt Tarceva™	Loperamide (4 mg at first onset, followed by 2mg every 2 – 4 hours until diarrhea free for 12 hours) and Interrupt Tarceva™ until resolution to Grade ≤ 1, and restart at reduced dose Appropriate rehydration
Grade 4	Discontinue Study	Loperamide (4 mg at first onset, followed by 2mg every 2 – 4 hours until diarrhea free for 12 hours) Appropriate rehydration
Rash		
Grade 1	None	Any of the following: minocycline ^a , topical tetracycline, topical clindamycin, topical silver sulfadiazine, diphenhydramine, oral prednisone (short course) at discretion of the investigator.
Grade 2	None	Manage as described above
Grade 3 (or intolerable Grade 2)	Dose reduction; dose can be re-escalated when rash is ≤ Grade 2	Manage as described above
Grade 4	Discontinue Study	Manage as described above

^a Recommended dose: 200 mg orally bid (loading dose) followed by 100 mg orally bid × 7–10 days.

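### Section 3.3 and Appendix 4 give conflicting erlotinib instructions for grade 3 and 4 diarrhea and rash, and nothing says which governs

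*Protocol*

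**What the plan says.** Protocol section 3.3 sets a single dose-adjustment rule for drug-related toxicity of grade 3 or above and names skin toxicity and diarrhea as included. Under it "the Tarceva will be paused till toxicity has resolved to a grade II or better". Treatment then restarts one level down: "The Tarceva will be resumed in a dose of 100 mg if the dose before pausing was 150 mg", and 50 mg if it was 100 mg. Erlotinib is not restarted only when the patient was already on 50 mg. Grade 4 has no separate rule. The section ends by pointing to Appendix 4 for managing erlotinib toxicity.

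Appendix 4 has its own column for changes to the study drug dose, and it covers the same two toxicities:

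- **Diarrhea, grade 3:** interrupt "until resolution to Grade ≤ 1, and restart at reduced dose".
- **Rash, grade 3 or intolerable grade 2:** "Dose reduction; dose can be re-escalated when rash is ≤ Grade 2".
- **Diarrhea or rash, grade 4:** "Discontinue Study".

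Section 8.3 adds a rule for two radiation complications: "In case of grade 3 or worse esophagitis or pneumonitis, the administration of Tarceva will be terminated for that patient". Section 3.3 sends the reader elsewhere for it: "For management of radiation complication during therapy see section 8.2".

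**The concern.** A site facing grade 3 or 4 diarrhea or rash finds two instructions in the same protocol and no statement of which applies. At grade 4 they point in opposite directions: section 3.3 re-exposes the patient once the event has improved, and Appendix 4 takes the patient off the drug.

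The two toxicities are not remote ones. Section 8.2 says "The most common, expected adverse events for Tarceva include: Rash, pruritus, dry skin, diarrhea". The toxicity stopping rule in section 6.3 is built on grade 4 pneumonitis or esophagitis and on unexpected severe toxicity, so it does not clearly cover expected rash or diarrhea. The individual dosing rule is therefore the main written safeguard for them.

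Several sites take part, each expected to enrol 3 to 15 patients (section 6.4). If they read the protocol differently, the same event will lead to different drug exposure, and toxicity is a secondary endpoint.

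**Working it through.** The protocol states no figure to reproduce. The check sets section 3.3 beside each grade 3–4 row of Appendix 4 and then looks for a statement of precedence.

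| Event | Section 3.3 | Appendix 4 | Where they part |
|---|---|---|---|
| Diarrhea, grade 3 | Pause to grade 2 or below, resume one level lower | Interrupt to grade 1 or below, restart at reduced dose | At grade 2, the first resumes and the second withholds |
| Rash, grade 3 | Pause to grade 2 or below, resume one level lower; no re-escalation provided | Reduce dose; re-escalation allowed at grade 2 or below | Pause or no pause; at grade 2 or below, restart lower or allow an increase |
| Diarrhea, grade 4 | Pause, then resume one level lower | Discontinue | Rechallenge or stop |
| Rash, grade 4 | Pause, then resume one level lower | Discontinue | Rechallenge or stop |

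**Count.** 4 of 4 grade 3–4 rows differ.

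**Size at grade 4.** The dose steps in section 3.3 are 150 → 100 → 50 mg → not resumed. The maximum number of resumptions is therefore 2 from 150 mg, 1 from 100 mg and 0 from 50 mg. Appendix 4 allows 0 from any dose.

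**Size at grade 3 diarrhea.** The restart thresholds are grade 2 and grade 1, one full grade apart.

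**Precedence.**
- The reference in section 3.3 to Appendix 4 follows a complete rule that already names skin toxicity and diarrhea. It does not say that the appendix overrides that rule.
- The texts cannot be divided into dosing (section 3.3) and supportive care (Appendix 4), because Appendix 4 has its own dosing column.
- Section 8.3 concerns only esophagitis and pneumonitis.
- Section 8.5 leaves rash care to institutional guidelines and gives no erlotinib dose rule.

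**A further gap in the rash row.** The row also covers intolerable grade 2 rash. Re-escalation is allowed at grade 2 or below, so for these patients the condition is already met at the moment the dose is reduced.

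**The case against.** The strongest defence is that section 3.3 is a general default, introduced as a recommendation, and Appendix 4 is the specific table to which it refers. Section 8.3 is naturally read in this way, as a specific exception, although no precedence is stated there either. On this view most clinicians would follow the table, and rechallenge after grade 4 would be unlikely in practice. That may well be so, but the reading is weaker for Appendix 4 because section 3.3 names the very two toxicities that the table covers. Calling the rule a recommendation does not help either: its operative sentences are worded as instructions, and two recommendations can still conflict.

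A second argument is that only the grade 4 rows truly contradict. A site that waits for grade 1 diarrhea has also passed grade 2, and a site that pauses for grade 3 rash and restarts lower has also reduced the dose. Such a site could stay close to both texts. It is fair that the grade 3 diarrhea row is the narrowest difference. However, section 3.3 says that the drug is resumed once grade 2 is reached, when Appendix 4 still withholds it. Appendix 4 also prescribes interruption for grade 3 diarrhea but only reduction for grade 3 rash, which suggests that the distinction is meant.

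Several points limit the size, and they stand:
- Two resumptions is a ceiling. It needs repeated events with recovery between them, within about 6.5 weeks of treatment.
- Section 8.2 lists rash and diarrhea without grade, so it does not show that grade 3–4 events will be common.
- Clinical events above grade 3 are serious adverse events under section 8.1 and reach the sponsor within one working day. This limits unnoticed divergence at grade 4, but it does not tell the site which dose rule to follow.
- CTC grading is the same under either rule. Only exposure, and any toxicity that follows from it, would differ.

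**Conclusion.** The concern holds. All four grade 3–4 rows of Appendix 4 differ from section 3.3, and the protocol does not say which text governs. The two grade 4 rows are a direct contradiction on rechallenge and would justify a correction on their own; the grade 3 differences are smaller but real.

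The conclusion rests on the wording alone. It does not depend on whether the grade 4 entry in Appendix 4 means stopping the drug or leaving the study, since neither fits with pausing and resuming. The number of the 57 patients affected is unknown, because no incidence of grade 3–4 diarrhea or rash is given. The sample size and the planned analysis are not affected. The point should be fixed for patient safety and for uniform drug exposure across sites.

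**What to change.** Amend section 3.3 to state that Appendix 4 governs diarrhea and rash, and that the pause-and-reduce rule applies to other drug-related toxicity of grade 3 or above. Then:

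1. **Grade 4 diarrhea or rash:** stop erlotinib permanently. Reword the Appendix 4 entry so that it means stopping the drug and not leaving the study.
2. **Grade 3 diarrhea:** restart at the reduced dose only at grade 1 or below.
3. **Grade 3 rash:** have the investigators settle one rule on pausing and re-escalation. It should also cover intolerable grade 2 rash, with a re-escalation condition that is not already met when the dose is reduced.
4. **Clarifications:** state that section 8.3 overrides section 3.3 for esophagitis and pneumonitis, and change the cross-reference in section 3.3 from 8.2 to 8.3.

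The cost is amendment wording and a note to sites. Sample size, visits and analysis do not change.

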4.1 Target volumes

GTV comprise the tumor as seen on the planning CT scan (the size after chemotherapy) plus any pathological lymph node during time before start of radiotherapy even if they have disappeared after induction chemotherapy.

CTV encompass the *GTV* plus the following margins: 1.0 cm in the mediastinum and 0.5 cm in lung tissue. The margins are modified if the *CTV* is close to the large vessels, bones, trachea or the thoracic wall, then the anatomic structures constitute the demarcation of the *CTV* as long as no invasion is seen in the surrounding tissue. For a primary in the lung, not involving the hilar region or the mediastinum, the *CTV* should not be expanded into the mediastinum. For lymph nodes not invading lung tissue, the *CRV* should not be expanded into healthy lung tissue.

No elective radiation will be used to unaffected lymph nodes.

ITV: If the treatment is based on a standard 3D CT scan without 4D planning, the following margins are used: *CTV* + 0.5 cm. *ITV* should be set to zero towards columna, apex and contralateral lung.

If a 4D CT scan is used for the treatment planning, it is allowed to create patient specific margins. In that case the treatment plan should be carried out on the mid-ventilation phase as described by Wolthaus et al. (13). The size of the margin related to the respiration shall be calculated as described by Van Herk et al. (14).

PTV margins should be based on experience related to type of fixation used in the clinic. If patient specific margins are to be used, a study of the size of *PTV* margin has to be performed at the institution. For the patient specific margins, the size of the *PTV* margin has to be calculated based on the same formalism as for the *ITV* (14). For patient specific margins it is important that *ITV* and *PTV* margins are not added linearly but as the square-root of the sum of the squares. Thus it might be beneficial to expand directly from *CTV* to *PTV*, so that the *ITV* is contained in the *PTV*, since most planning systems only supports linear addition of margins. If patient specific margins are applied, it is important to report the size of the margin (appendix 5).

4.2 Doses to organs at risk

The dose to the lungs, spinal cord, heart, and esophagus must be reported. In the treatment of lung cancer with combination treatments the dose the constraints to the organs at risk are given as:

1. Both lungs must be outlined: $V_{20} \leq 40\%$ i.e. a maximum of 40% of the lungs (outside the *GTV*) may receive a dose exceeding 20 Gy or more.
2. The spinal cord must be outlined as the spinal canal: The dose must not exceed 45 Gy.
3. The whole of the heart must be outlined: $V_{50} \leq 20\%$.
4. Esophagus through out the thorax: 66 Gy as a maximum dose.

5. Study population

The study population is patients with NSCLC stage IIB - IIIB without pleural effusion suitable for curatively intended irradiation and concomitant Tarceva.

5.1 Inclusion criteria

Patients must meet *all* of the following inclusion criteria to be eligible for participation in this program.

- Age ≥ 18 years
- Patients with histologically or cytologically documented diagnosis locally advanced NSCLC stage IIB to IIIB without pleural effusion
- Performance status ≤ 2 on the ECOG scale
- Serum bilirubin must be ≤ 1.5 upper limit of normal (ULN)
- ALAT $\leq 2 \times$ ULN
- Able to comply with study and follow-up procedures

- Patients with reproductive potential must use effective contraception
- Written (signed) informed consent to participate in the study

5.2 Exclusion criteria

Patients who meet *any* of the following exclusion criteria are not to be enrolled in this study:

- Any unstable systemic disease (including active infection, unstable angina, congestive heart failure, severe hepatic, renal, or metabolic disease)
- Any other malignancies within 5 years (except for adequately treated carcinoma in situ of the cervix or basal or squamous cell skin cancer)
- Inability to take oral medication, or requirement of intravenous alimentation
- Nursing mothers

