5.3 Monitoring during therapy

The patient may receive induction chemotherapy before inclusion in the study, and is as such not part of the study. The patients cannot be included in the study before a plan has been worked out showing that curatively intended radiation is possible, and informed consent has been obtained (Fig. 1).

	Screening/ Baseline	Treatment Period Timing	Day 30-45 after stop of treatment
Informed Consent	x	-	-
Demographics	x	-	-
Medical history	x	-	-
Physical examination	x	Weekly	x
Body weight	x	Weekly	x
Laboratory ¹	x	Weekly	x
ECG	x	-	x
Lung functions test ²	x	-	x
Lung CO diffusion test	x	-	-
CT scan thorax and upper abdomen	x	-	x
Tumor measurements	x	-	x
PET-CT ³	x	-	-
CT scan brain ⁴	x ⁴	-	-
Performance Status (PS)	x	Weekly	x
Side effects ⁵	-	Recorded weekly	x
Study drug compliance ⁶	-	x	x
Smoking status	x	Recorded Weekly	x

¹ Hematology: Hemoglobin, WBC, granulocytes and platelet count, INR (Only for patients receiving warfarin or coumarin-derivative). Biochemistry: Alkaline phosphatase, Serum bilirubin, Serum creatinine, ALAT (SGPT), LDH. Only laboratory abnormalities linked to unexpected clinical symptoms will be documented in the CRF.

² FEV₁/FVC test. If neoadjuvant chemotherapy, the test must be performed after cessation of chemotherapy.

³ CT scans, PET CT scans per institutional standards, EBUS or mediastinoscopy may be accepted as mediastinal evaluation if PET-CT is not available

⁴ If no PET-CT available

⁵ Side effects to be recorded according to CTC version 3.0

⁶ Pharmacy log

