8.1 Serious adverse events (SAEs)

An SAE is defined as an AE that meets one of the following conditions:

- Death during the period of protocol defined surveillance
- Life-threatening event (defined as a patient at immediate risk of death at the time of the event)
- An event requiring inpatient hospitalisation or prolongation of existing hospitalisation during the period of protocol defined surveillance with the exception of treatment-related enteritis or fatigue, leucopenia, thrombocytopenia or hospitalization due to treatment administration or other elective measures
- Results in congenital anomaly or birth defect
- Results in a persistent or significant disability/incapacity
- Any other important medical event that may not result in death, be life threatening, or require hospitalisation, may be considered a serious adverse experience when, based upon appropriate medical judgment, the event may jeopardize the patient and may require medical or surgical intervention to prevent one of the outcomes listed above. Examples of such medical events include allergic bronchospasm requiring intensive treatment in an emergency room or at home, blood dyscrasias or convulsions that do not result in inpatient hospitalisation, or the development of drug dependency or drug abuse.

In this study unexpected and related SAEs are defined as adverse reactions with at least a possible relationship to study therapy that are not consistent with the approved summary of product

characteristics (SPC) and which to their nature are serious. The SPC is available at:
www.emea.europa.eu

All SAEs will be recorded on the appropriate SAE CRF, followed through resolution by the investigator, and reviewed and evaluated by the Medical Monitor

Abnormal laboratory values and clinical adverse events will be reported as SAEs if they are graded higher than 3 on the CTC v3.0.

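### Section 5.2 excludes nursing mothers but does not name pregnancy, and no pregnancy test is scheduled, so a patient with an existing, especially unrecognised, pregnancy can meet every listed criterion

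*Protocol*

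**What the plan says.** Section 5.2 opens with a strict rule: "Patients who meet *any* of the following exclusion criteria are not to be enrolled in this study". Four exclusions follow. They cover unstable systemic disease, another malignancy within five years, inability to take oral medication or need for intravenous feeding, and "Nursing mothers". Pregnancy is not among them.

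Section 5.1 lists eight inclusion criteria. The only one on reproduction is "Patients with reproductive potential must use effective contraception". Age is bounded only from below, at 18 years, and there is no restriction by sex or menopausal status.

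Section 5.3 gives the screening and treatment schedule. Its laboratory footnote itemises a blood count, INR for patients on warfarin-type drugs, and then "Biochemistry: Alkaline phosphatase, Serum bilirubin, Serum creatinine, ALAT (SGPT), LDH". The follow-up schedule in section 5.4 repeats the same panel.

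Section 5 introduces the criteria by describing the population as patients "suitable for curatively intended irradiation and concomitant Tarceva".

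On exposure, section 3.2 says "Tarceva will start at the day of the radiation in daily dose of 150 mg", continued for about 6.5 weeks. Section 4 prescribes 66 Gy in 33 fractions.

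Section 8.1 counts an event as serious if it "Results in congenital anomaly or birth defect".

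**The concern.** The protocol shows in three places that harm to an infant or fetus is on its mind: it bars breastfeeding patients, it requires contraception, and it classes a birth defect as serious. It does not state the one condition that links these, namely that the patient is not pregnant when she enters. An exclusion list that names lactation and leaves out pregnancy reads like an oversight.

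What is at stake is an enrolment rule that bears on safety. Eligibility at each site is checked against the lists in 5.1 and 5.2 and the baseline items in 5.3. If none of these names or tests for pregnancy, whether a pregnancy is found before treatment depends on local habit. Section 6.4 expects each site to include between 3 and 15 patients, so that habit need not be uniform. Nothing in the estimation or testing of the primary endpoint is involved.

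**Working it through.** No calculation applies, and the plan states no figure on this point. The check is to place the relevant sections side by side and ask of each whether it bars an existing pregnancy and whether it would detect one.

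| Protocol text | Bars an existing pregnancy? | Detects one? |
|---|---|---|
| 5.2, four exclusion bullets | No; 0 of 4 name it | No |
| 5.1, eight inclusion bullets | Not expressly; 0 of 8 name it | No; no negative test is required |
| 5.3, baseline and weekly schedule with laboratory footnote | Not applicable | No dedicated test |
| 5.4, follow-up schedule with laboratory footnote | Not applicable | No dedicated test |
| 5, population statement | Only through the investigator's general judgement | No |
| 8.1, serious adverse event categories | No; this is reporting, not eligibility | No |

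1. **Exclusion list.** Any one listed item bars enrolment. A condition that is not listed does not bar it under this rule, and pregnancy is not listed.

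2. **Contraception criterion.** It has to be met for entry, so it makes the investigator consider reproductive status. Its content is what the patient does to avoid conceiving. A patient may have conceived before she began contraception, or despite it, and still satisfy the criterion. It is a partial safeguard that neither names nor tests for an existing pregnancy.

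3. **Baseline schedule.** The laboratory items are listed one by one, so a pregnancy test cannot be read into a general heading. Blood is already drawn at screening, so the means of testing is at hand.

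4. **Population statement.** A judgement of suitability can be exercised only on what is known. It gives a basis for declining a known pregnancy and none for finding an unknown one.

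5. **Rest of the protocol.** The words *pregnant* and *pregnancy* appear nowhere in the text shown. The nearest wording is the birth-defect category in 8.1.

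Taken together, a pregnant patient **can** meet all eight inclusion criteria and none of the four exclusions. The clearest case is a pregnancy that nobody has recognised.

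**The case against.** The strongest reply is that the protocol is not silent on the matter when read as a whole. Contraception is a condition of entry. Section 5 limits the population to patients fit for curative irradiation with the study drug, and section 5.3 forbids inclusion until a plan shows that such irradiation is possible. Medical history and physical examination are baseline items, and examination and body weight recur weekly during treatment. A competent investigator would not enrol a woman known to be pregnant.

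Much of this stands, and it rules out several stronger readings that a reader might infer:

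- *That the protocol, followed to the letter, admits a known pregnancy.* This ignores the population statement in section 5, which lets the investigator decline. For a known pregnancy the fair criticism is that the wording is unclear.
- *That every pregnant patient meets all the criteria.* The text supports only that she can.
- *That the contraception rule applies only from enrolment onwards.* Section 5.1 does not say so; it states the rule as an eligibility condition.
- *That no later step could reveal a pregnancy.* Scheduled examinations and weight checks might. The supportable statement is that no dedicated test is scheduled, and that these checks could miss an early pregnancy.
- *That 8.1 captures a pregnancy only once a birth defect has occurred.* The category for other important medical events leaves room for judgement. What is absent is an explicit rule.

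The reply does not close the gap for an unrecognised pregnancy. None of the safeguards it lists is designed to find one. Nor is this a matter for a statistical analysis plan, which does not set eligibility or visit content. Pages removed from the public copy may mention pregnancy, but an information sheet would not add a criterion to 5.2 or a test to 5.3, and both appear complete here.

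**Conclusion.** The point holds in a limited form. Sections 5.1 to 5.3 together neither name pregnancy as a bar nor schedule a test for it, and no other section supplies what is missing. The consequence is that an existing pregnancy, chiefly an unrecognised one, can pass the written entry rules.

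The size cannot be derived from the documents, which give no age or sex distribution. A reader might be tempted to put a number on it. If one assumed that 2% to 5% of the 57 planned patients were women of childbearing potential, that would be 57 × 0.02 = 1.1 to 57 × 0.05 = 2.9 women. That share has no support in the protocol, and the result counts women who could be pregnant, not pregnancies, which would be far fewer. It also does not show that such women would go unchecked, since history-taking is scheduled. The number affected should be treated as unknown and probably very small.

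The case for acting rests on the seriousness of a fetal exposure, which 8.1 itself recognises, and on the small cost of the remedy. No endpoint, sample size, error rate or analysis is affected. The conclusion assumes only that the eligibility lists and visit tables are complete as shown.

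**What to change.** Reconcile sections 5.1, 5.2 and 5.3 with two short edits:

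1. In 5.2, change the last bullet to *Pregnant or nursing women*.
2. In 5.3, add a pregnancy test for women of childbearing potential to the baseline laboratory item, using the blood sample already taken at screening.

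The cost is an amendment to two sections and one laboratory test in what is likely to be very few patients. No extra visit or sample is needed.

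As a side note, if the protocol is being amended anyway, section 8.1 could state explicitly how a pregnancy on study is to be reported to the sponsor. That would be a third edit and a new reporting duty. It is separate from the eligibility gap, which the first two edits close on their own.
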